4.2.3 Functional Assessment of Upper and Lower Limbs

Functional assessment of both the upper and lower extremities will be assessed at at Week 1, every 3 months (Week 12, 24, etc), and 1-Week Post-treatment Follow-up. Upper extremity muscle function will be measured using the Brooke scale. The grading for the Brooke scale is provided below:

Brooke Scale	Description
• 1	Starting with arms at the sides, the patient can abduct the arms in a full circle until they touch above the head
• 2	Can raise arms above head only by flexing the elbow (shortening the circumference of the movement) or using accessory muscles
• 3	Cannot raise hands above head, but can raise an 8-oz glass of water to the mouth
• 4	Can raise hands to the mouth, but cannot raise an 8-oz glass of water to the mouth
• 5	Cannot raise hands to the mouth, but can use hands to hold a pen or pick up pennies from the table
• 6	Cannot raise hands to the mouth and has no useful function of hands

Lower extremity muscle function will be measured using the Vignos scale. The grading for the Vignos scale is provided below:

Vignos Scale	Description
• 1	Walks and climbs stairs without assistance
• 2	Walks and climbs stair with aid of railing
• 3	Walks and climbs stairs slowly with aid of railing (over 25 seconds for eight standard steps)

- 4 Walks unassisted and rises from chair but cannot climb stairs
- 5 Walks unassisted but cannot rise from chair or climb stairs
- 6 Walks only with assistance or walks independently with long leg braces
- 7 Walks in long leg braces but requires assistance for balance
- 8 Stands in long leg braces but unable to walk even with assistance
- 9 Is in a wheelchair
- 10 Is confined to a bed

Scores for both the upper and lower extremity muscle function assessments will be considered as an ordinal variable.

4.2.4 Individualized Neuromuscular Quality of Life (INQoL)

The Individualized Neuromuscular Quality of Life (INQoL) is a validated, muscle disease specific measure of quality of life (QoL). The self-administered questionnaire consists of 45 items divided into 14 domains: 7 symptom impact domains (weakness, pain, fatigue, locking [i.e., myotonia], droopy eyelids, double vision, and swallowing difficulties); 5 life domains (activities, independence, relationships, emotions, and body image); and 2 treatment impact domains. All responses for individual questions are measured using a 7-point Likert scale. The 7 symptom impact domains and the 5 life domains are calculated as a percentage of the maximum detrimental impact with a higher percentage indicating a greater symptom impact or worse QoL. There are 2 scores calculated for the treatment impact domain, the perceived treatment effect and the expected treatment effect. The INQoL domains calculated are provided below:

Symptom Impact Domains	Life Domains	Treatment Impact Domains

 • Weakness • Pain • Fatigue • Locking • Droopy eyelids • Double vision • Swallowing difficulties 	
 • Activities • Independence • Social relationships • Emotions • Body image 	
 • Perceived treatment • Expected treatment

Additionally, a QoL score is calculated from questions 5, 6, and 7 from Section 1 and questions 1 and 2 from Section 2. Scoring of the domains is provided below:

Domain	Scoring Procedure	Missing Data Rules
Section 1 Questions (Symptom Impact Domains)		
Weakness	$[(1a+1b+1c)/19]*100$	If Part A (Yes/No Question) and Part B is missing, then score = 0. Part B missing: If a missing, then score = 1 If b missing, then impute previous value (a) If c missing, then score = 0
Pain	$[(2a+2b+2c)/19]*100$	
Fatigue	$[(3a+3b+3c)/19]*100$	
Locking	$[(4a+4b+4c)/19]*100$	
Droopy eyelids	$[(5a+5b+5c)/19]*100$	
Double vision	$[(6a+6b+6c)/19]*100$	
Swallowing difficulties	$[(7a+7b+7c)/19]*100$	

Domain	Scoring Procedure	Missing Data Rules
Section 2 Questions (Life Domains)		
Activities	Question 1: $([4*(AI+AII+AIII)]+[3*(BI+BII)]/108)*100$ Note: If not working due to condition AIII=6 Note: If retired/unemployed/work in home not due to condition, then $([6*(AI+AII)]+[3*(BI+BII)]/108)*100$	If an A item is missing, sum completed items and multiply by 6 if two items completed and 12 if only one item has been completed (to get score out of 72) AIII = 6 if not working due to your condition = "YES" If BI missing, then impute average of completed activity items from A If BII missing, then score = 0
Independence	Question 2: $([12*A]+[3*(BI+BII)]/108)*100$	If A missing, then score = 0 If BI missing, then impute value from A If BII missing, then score = 0
Social relationships	Question 3: $([3*(AI+AII+AIII+AIV)]+[BI+BII+BIII+BIV+BV+BVI]/108)*100$ Note: If AI not applicable, then $([4*(AII+AIII+AIV)]+[BI+BII+BIII+BIV+BV+BVI]/108)*100$	If A missing, sum completed items and multiply by 4 if three completed items, 6 if two completed items, and 12 if one completed item If BI missing, impute average of A items (Relationship with spouse/partner AI and Relationship with other family members AII) If BII missing, then score = 0 If BIII missing, then impute value from Friends item (AIII) If BIV missing, then score = 0 If BV missing, then impute value from Other People (AIV) item If BVI missing, then score = 0
Emotions	Question 4: $([3*(AI+AII+AIII+AIV)]+[3*(BI+BII)]/108)*100$	If A item missing, sum the completed items and multiply by 4 if three completed items, 6 if two completed items, and 12 if one completed item

Domain	Scoring Procedure	Missing Data Rules
		If BI missing, then impute average of items completed in A If BII missing, then score = 0
Body image	Question 5: $([12*A]+[3*(BI+BII)]/108)*100$	If A missing, then score = 0 If BI missing, then impute value from A If BII missing, then score = 0
QoL	Add scores of items in Part B for Questions 1 through 5 in Section 2 with the following corrections: 3*(BI+BII) for Questions 1, 2, 4, and 5 BI+BII+BIII+BIV+BVBVI for Question 3 Divide the total score by 180 and multiply by 100	
Section 3 Questions (Treatment Impact Domains)		
Perceived treatment effects	$([AI+AIII)-(BI+BIII)]/12)*100$	If AI missing, then score = 0 If AIII missing, then score = 0 If BI missing, then score = 0 If BIII missing, then score = 0
Expected treatment effects	$([AII+AIII)-(BII+BIII)]/12)*100$	If AII missing, then score = 0 If AIII missing, then score = 0 If BII missing, then score = 0 If BIII missing, then score = 0

The INQoL will be collected at at Week 1, every 3 months (Week 12, 24, etc), 1-Week Post-treatment Follow-up, and 12-Week Post-treatment Follow-up. The domains and total score will be considered as continuous data.

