8.4.1.5. INQoL

The INQoL is a validated, muscle-disease-specific measure of quality of life. The self-administered questionnaire consists of 45 questions within 10 sections. Four sections focus on the impact of key muscle disease symptoms (weakness, locking [i.e., myotonia], pain, and fatigue); 5 sections focus on the impact (degree and importance of impact) muscle disease has on particular areas of life; and the remaining section focuses on the

positive and negative effects of treatment.⁵⁶ Patients will complete the InQoL at the time points designated in [Table 1](#).

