8.2 Missing Data Conventions

Rules for partial dates are provided in Appendices 2 and 3. These rules will apply to adverse events and medications. Missing values for other variables will not be imputed.

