14.3.3 INQoL Domains and QoL Score by Visit (Safety population Cumulative)

Disease Study Visit	Score = QoL								
	Actual			Change From Baseline			Percent Change from Baseline		
	N	Mean (SD)	Median (Min, Max)	N	Mean (SD)	Median (Min, Max)	N	Mean (SD)	Median (Min, Max)
Total (N = xx)									
Parent Study									
Baseline	xx	xx.x (xx.xx)	xx.x (xx, xx)						
Week 14/1-Week Follow-up	xx	xx.x (xx.xx)	xx.x (xx, xx)	xx	xx.x (xx.xx)	xx.x (xx, xx)	xx	xx.x (xx.xx)	xx.x (xx, xx)
Current Study (ATYR1940-C-006)									
Week 1	xx	xx.x (xx.xx)	xx.x (xx, xx)	xx	xx.x (xx.xx)	xx.x (xx, xx)	xx	xx.x (xx.xx)	xx.x (xx, xx)
Week 12	xx	xx.x (xx.xx)	xx.x (xx, xx)	xx	xx.x (xx.xx)	xx.x (xx, xx)	xx	xx.x (xx.xx)	xx.x (xx, xx)
...									
1-Week Post-treatment Follow-up	xx	xx.x (xx.xx)	xx.x (xx, xx)	xx	xx.x (xx.xx)	xx.x (xx, xx)	xx	xx.x (xx.xx)	xx.x (xx, xx)
12-Week Post-treatment Follow-up	xx	xx.x (xx.xx)	xx.x (xx, xx)	xx	xx.x (xx.xx)	xx.x (xx, xx)	xx	xx.x (xx.xx)	xx.x (xx, xx)
...									
<repeat for>									
EO-FSHD (N = xx)									
FSHD (N = xx)									
LGMD2B (N = xx)									

Note: FSHD=Facioscapulohumeral muscular dystrophy; LGMD2B=Limb-girdle muscular dystrophy 2B; EO-FSHD=Early Onset Facioscapulohumeral muscular dystrophy

Note: Baseline is defined as the baseline in the parent study.

Source: Listing xx.x.xx, Dataset: [NAME], Program: xxxxxx.sas, Output: T_14_3_3_XXXXX.rtf, Generated on: DDMMMYYYY HH:MM

Page x of y

Programming Note: Include all domains in the following order: QoL, Weakness, Pain, Fatigue, Muscle Locking, Droopy eyelids, Double vision, Swallowing difficulties, Activities, Independence, Social Relationships, Emotions, Body Image, Perceived Treatment Score, and Expected Treatment Score.

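### SAP 4.2.4 divides only the Part B term of each INQoL life-domain score by 108, and its seven-symptom, 45-item description does not match the protocol's four-symptom form

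*SAP*

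**What the plan says.** **Protocol 8.4.1.5, item count.** The "questionnaire consists of 45 questions within 10 sections".

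**Protocol 8.4.1.5, make-up of the sections.** On symptoms, the protocol is specific: "Four sections focus on the impact of key muscle disease symptoms (weakness, locking [i.e., myotonia], pain, and fatigue". Of the rest, five cover areas of life and one covers treatment, so 4 + 5 + 1 = 10.

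**SAP 4.2.4, description.** "The self-administered questionnaire consists of 45 items divided into 14 domains: 7 symptom impact domains". The three additional symptoms are droopy eyelids, double vision and swallowing difficulties. The programming note to Table 14.3.3 carries them through ("QoL, Weakness, Pain, Fatigue, Muscle Locking, Droopy eyelids, Double vision, Swallowing difficulties, Activities, Independence"), and Listing 16.2.21 has fields for them. The text says that symptom and life scores express the share of the greatest possible detrimental impact, so they should lie between 0 and 100%.

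**SAP 4.2.4, life-domain scoring.** After its two opening brackets, the Activities formula reads "4*(AI+AII+AIII)]+[3*(BI+BII)]/108)*100". The other four life domains, and the alternates for Activities and Social relationships, are laid out the same way.

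**Missing data.** For a blank symptom block SAP 4.2.4 says: "If Part A (Yes/No Question) and Part B is missing, then score = 0". SAP 8.2, after its rules for partial dates of adverse events and medications, says: "Missing values for other variables will not be imputed".

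**The concern.** There are two separate faults in one scoring section.

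The first is in an operative rule. Division by 108 is attached to the Part B bracket and not to the sum, so Part A enters unscaled. Code that follows the SAP literally would give life-domain scores in the hundreds or thousands of percent. It would also distort the balance between the two parts.

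The second is a conflict about which questionnaire is being scored. The SAP keeps the protocol's item count but adds three symptoms. A programmer or reader cannot tell from the documents which domains were collected, or how to treat a domain that was not on the form.

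**Working it through.** **1. Item coding.** SAP 4.2.4 uses a 7-point response scale. It sets the Activities work item to 6 when the patient is not working because of the condition, and its missing-item rule puts the Activities Part A total on a 72-point scale. With three items weighted by 4, 4 × (3 × 6) = 72, so items run from 0 to 6. Part B of Activities then has a maximum of 3 × (6 + 6) = 36, and 72 + 36 = 108. The 108 is therefore the maximum of the whole sum.

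**2. Life-domain maxima.** As printed: (A + B/108) × 100. Intended: (A + B)/108 × 100.

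| Formula | Part A max | Part B max | Printed max | Intended max | One Part A item at 1, rest 0: printed (intended) |
|---|---|---|---|---|---|
| Activities | 4 × 18 = 72 | 3 × 12 = 36 | 7,233% | 100% | 400% (3.7%) |
| Activities, alternate | 6 × 12 = 72 | 3 × 12 = 36 | 7,233% | 100% | 600% (5.6%) |
| Independence | 12 × 6 = 72 | 3 × 12 = 36 | 7,233% | 100% | 1,200% (11.1%) |
| Social relationships | 3 × 24 = 72 | 6 × 6 = 36 | 7,233% | 100% | 300% (2.8%) |
| Social relationships, alternate | 4 × 18 = 72 | 6 × 6 = 36 | 7,233% | 100% | 400% (3.7%) |
| Emotions | 3 × 24 = 72 | 3 × 12 = 36 | 7,233% | 100% | 300% (2.8%) |
| Body image | 12 × 6 = 72 | 3 × 12 = 36 | 7,233% | 100% | 1,200% (11.1%) |

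The printed value stays at or below 100% only if every Part A item is 0. Its maximum is then 36/108 × 100 = 33.3%. At the overall maximum, Part B supplies 33.3 of 7,233.3 points (0.46%), where the intended share is 36/108 = 33.3%. Rescaling afterwards would not restore the score.

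**3. The other denominators.** The overall QoL row divides by 180, and 4 × 36 + 36 = 180. The symptom rows divide by 19, which equals 7 + 6 + 6 if item a runs to 7. That is an assumption, though it fits the rule that sets a missing item a to 1. Both reach exactly 100%, so the bracket fault is confined to the life domains.

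**4. Item count from the SAP's scoring rows.**
- Life: Activities 5 + Independence 3 + Social relationships 10 + Emotions 6 + Body image 3 = 27.
- Treatment: AI, AII, AIII, BI, BII, BIII = 6.
- Symptoms: 3 scored items each (a, b, c).
- Four symptoms: 12 + 27 + 6 = 45, which reproduces the stated figure.
- Seven symptoms: 21 + 27 + 6 = 54, which is 9 more than stated.

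Adding one Yes/No gate per symptom gives 49 and 61. Any seven-symptom count that includes every scored item is at least 54.

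**5. The zero rule beside the other rules.** SAP 4.2.4 sets a blank symptom block to 0. SAP 8.2 and Protocol 9.2.3 rule out imputation. SAP 6.0 gives no change from baseline where no baseline value was recorded. None of them says what to do with a question that is not on the form.

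**The case against.** **The formula fault is one of notation.** The intended formula can be recovered from the text, a score of several thousand percent would stand out in a percentage column, and SAP version 2.0 followed comments on a dry run. The same table has other slips: unbalanced brackets in the treatment formulas and a missing plus sign in the QoL row. This lowers the chance that wrong values reach a report. It does not make the rule right. The life-domain brackets balance as printed, so a character lost in PDF reading is not an obvious cause.

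**The item match depends on how items are counted.** The documents do not say whether gate questions count. The match at 45 therefore supports a four-symptom source for the figure, but does not show which form patients completed. Listing 16.2.21 has field-level columns for questions 5, 6 and 7, and the SAP says it should be read with CRF version 1.0. The 45 may simply have been carried over from the protocol. That stands, and it leaves one of the two documents in need of correction either way.

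**A reader might infer more:** that Table 14.3.3 will show three domains as all zeros, or a false worsening from a zero baseline (for example 0 to 1/19 = 5.3%, or 0 to 100%). The documents do not support this. It needs a form without questions 5 to 7 and the zero rule applied to questions never asked. No section shows that the parent and extension forms differ, and SAP 1.1, which lists several collection differences, does not mention the INQoL. SAP 6.0 and 8.2 point to missing values for unasked questions.

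**Conclusion.** The formula fault holds without conditions: seven printed formulas covering five domains have a maximum of 7,233% where the SAP's own description implies 100%. The 0 to 6 item coding behind those figures follows from the SAP's own rules.

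The conflict between documents is also real: four symptoms and 45 questions in the protocol, against seven symptoms and a stated 45 items in the SAP, whose rows add up to 54. Which form was used is unknown without the CRFs, and the listing shells lean towards seven symptoms. Structural zeros and false change remain a conditional risk, which clear wording would remove.

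The reach is limited. Quality of life is exploratory, Protocol 3.2.4 says that no specific endpoints were defined for it, no hypothesis test is planned, and up to 24 patients are expected. The overall QoL score has its own formula and is not touched by the bracket fault. No safety conclusion depends on this point.

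**What to change.** 1. In SAP 4.2.4, bracket each whole numerator before dividing:
   - Activities: `{[4*(AI+AII+AIII)] + [3*(BI+BII)]}/108*100`; alternate: `{[6*(AI+AII)] + [3*(BI+BII)]}/108*100`
   - Independence and Body image: `{[12*A] + [3*(BI+BII)]}/108*100`
   - Social relationships: `{[3*(AI+AII+AIII+AIV)] + [BI+BII+BIII+BIV+BV+BVI]}/108*100`; in the alternate, the first term is `[4*(AII+AIII+AIV)]`
   - Emotions: `{[3*(AI+AII+AIII+AIV)] + [3*(BI+BII)]}/108*100`
2. Confirm that the existing code uses these forms and that every life-domain score lies between 0 and 100.
3. Check the INQoL pages of the CRFs for 003, 004 and 006. If the form has four symptoms, remove the three extra domains from SAP 4.2.4, Table 14.3.3 and Listing 16.2.21. If it has seven, correct the item count and clarify Protocol 8.4.1.5.
4. State that the zero rule applies to unanswered questions only, as an exception to SAP 8.2, and that a domain not on the form at a visit is missing, with no change from baseline.

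The cost is a correction to the SAP and shells, a one-line protocol clarification if needed, and a CRF check. No new data are required. The final SAP version that SAP 1.0 foresees before database lock is the natural place for it.

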6.0 Definitions

Age

Age will be recorded on the CRF and not derived for this study.

Baseline

Baseline is defined as the baseline in the parent study.

Analyses of changes from pre-infusion to post-infusion (i.e., vital signs, and ECG) will use pre-infusion as well, when applicable. Post baseline values for tabulations will exclude unscheduled visit values; however, unscheduled visit values will be included in listings.

Change from Baseline

Change from baseline (CFB) will be calculated as (post-baseline – baseline). CFB will be calculated for patients with both a baseline and post-baseline value as applicable. Percent CFB will be calculated as (CFB/baseline)*100, where applicable.

If a baseline value has not been recorded for a parameter, then CFB will not be calculated for that parameter. Patients with missing CFB values will be excluded from analyses in which CFB is the endpoint.

Change from pre-infusion

Change from pre-infusion will be calculated as (post-infusion – pre-infusion). Change from pre-infusion will be calculated for patients with both pre-infusion and post-infusion values, as applicable. No imputation will be done for missing values.

Completion of study

A patient will be considered completed in the study when an End of Study CRF page indicates a completion date.

Concomitant medications

Concomitant medications are defined as any medications taken on or after the date of first date of infusion in the parent study. This includes medications that are ongoing at the time of first infusion.

Discontinuation of study

A patient will be considered discontinued from the study when an End of Study CRF page is completed indicating primary reason for discontinuation.

Prior medication

Prior medications are defined as any medications with start and stop dates prior to the date of first date of infusion in the parent study or an ongoing medications with a start date prior to first date of infusion in the parent study.

Protocol deviation

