16.2.21 Individualized Neuromuscular Quality of Life (INQoL) (Safety Population Cumulative)

Part 7

Patient ID/ Age/Race/Ethnicity/Sex	Disease	Visit	Perceived Treatment Score									Score (%)
			1A	1A.I	Not yet receive treatment	Unsure	1A.III	1B.I	Not yet receive treatment	Unsure	1B.III	
xxxxxxxxxx/xx/x/x/x	FSHD	xxxxxxxx	xxx	x	xxx	xxx	xx.x	xxx	xxx	xxx	xxx	xx.x

Note: FSHD=Facioscapulohumeral muscular dystrophy; LGMD2B=Limb-girdle muscular dystrophy 2B; EO-FSHD=Early Onset Facioscapulohumeral muscular dystrophy
 Note: W = white; B = black, African American or of African heritage; P = native Hawaiian or other Pacific islander; A = Asian; I = American Indian or Alaska native; O = Other; H = Hispanic or Latino; N = not Hispanic or Latino; M = male; F = female.
 Source: Dataset: [NAME], Program: xxxxxx.sas, Output: xxxx.rtf, Generated on: DDMMYYYY HH:MM
 Page x of y

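### The missing-equals-zero rule for the INQoL perceived treatment score can invent a pre-treatment baseline, from which Table 14.3.3 then reports change and percent change

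*SAP*

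**What the plan says.** SAP 4.2.4 defines two treatment impact scores. The perceived score is built as "AI+AIII)-(BI+BIII)]/12)*100" and the expected score as "AII+AIII)-(BII+BIII)]/12)*100" (the opening brackets fall outside the quoted runs). For the perceived score the missing-data column begins "If AI missing, then score = 0", and the same wording is repeated for AIII, BI and BIII. The expected score has the matching set for its own items.

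Listing 16.2.21 shows what the form collects. Part 7 (perceived) has columns for "Not yet receive treatment" and for being unsure beside both 1A.I and 1B.I. Part 8 (expected) has only the unsure column beside 1A.II and 1B.II. SAP 4.2.4 contains no scoring rule for either box.

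SAP 6.0 states: "Baseline is defined as the baseline in the parent study". SAP 9.7.2 asks for observed values, change and percent change for the INQoL domains. The programming note to Table 14.3.3 ends its list of rows with "Perceived Treatment Score, and Expected Treatment Score", so both scores receive all three summaries.

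Three general statements also bear on this. SAP 6.0 withholds change from baseline when no baseline was recorded. SAP 8.2 allows imputation only for partial dates. Protocol 9.2.3 allows none.

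**The concern.** The parent-study baseline precedes ATYR1940. Protocol 9.2.1 describes it as the latest assessment before the first study drug dose, and the laboratory, ECG and vital-sign shells in the SAP place it before the first ATYR1940 dose. That is the visit at which a patient could properly tick the not-yet-treated box. The tick says that there is no perceived effect to rate. Under the only rule available, it becomes a zero on AI and BI while AIII and BIII still count, and the result is stored as a score. The safeguard in SAP 6.0 does not act, because a number now sits in the baseline field.

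Section 2 of the same scoring table shows that the authors knew how to handle structural non-answers. It reweights the activities domain for people who are out of work for other reasons, and the relationships domain when the spouse item does not apply. Section 3 has no counterpart.

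What is at stake is one score in an open-label study, but it is the score that asks patients directly what treatment has done for them. A change in it is easy to quote.

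**Working it through.** **Inputs.** Formulas and missing rules: SAP 4.2.4. Boxes: Listing 16.2.21, Parts 7 and 8. Item scale: "All responses for individual questions are measured using a 7-point Likert scale". Coding for Section 3 is not stated. A Section 2 note, "Note: If not working due to condition AIII=6", points to a maximum of 6.

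**Reproducing the divisor of 12.**
- Items coded 0 to 6: largest numerator = (6 + 6) − (0 + 0) = 12.
- Items coded 1 to 7: largest numerator = (7 + 7) − (1 + 1) = 12.

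Both codings reproduce 12, and the full score runs from −100% to +100%. The Section 2 divisors favour 0 to 6: 4 × 18 + 3 × 12 = 108 for activities, and 4 × (3 × 12) + 36 = 180 for the QoL score.

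**Box ticked, AI = BI = 0 by rule.** Score = (AIII − BIII)/12 × 100.
- AIII at the top, BIII at the bottom: (6 − 0)/12 × 100 = +50%.
- AIII = 6, BIII = 3: 3/12 × 100 = +25%.
- AIII at the bottom, BIII at the top: (0 − 6)/12 × 100 = −50%.
- Range: −50% to +50%, the same under 1-to-7 coding because (7 − 1)/12 and (1 − 7)/12 give the same limits.
- Of the 7 × 7 = 49 combinations of AIII and BIII, 7 are ties, so 49 − 7 = 42 give a nonzero score.
- All four items blank: 0/12 × 100 = 0%.

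**Effect on change.** Take one later visit with AI = 3, AIII = 6, BI = BIII = 0, which scores 9/12 × 100 = +75%. At baseline the box is ticked.

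| Baseline AIII, BIII | Baseline score | Change | Percent change |
|---|---|---|---|
| 6, 0 | +50 | 75 − 50 = +25 | 25/50 = +50% |
| both blank | 0 | 75 − 0 = +75 | undefined |
| 0, 6 | −50 | 75 − (−50) = +125 | 125/(−50) = −250% |

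One later answer gives three different changes, none of them measured from a rated baseline.

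**Percent change without any box ticked.** The scale passes through zero, so the problem does not depend on the boxes. A fully answered baseline of −25 and a later +25 is a gain of 50 points, reported as 50/(−25) × 100 = −200%. This applies to the expected score as well.

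**If the rule means that the whole domain is 0.** Then ±50% cannot occur, but a baseline of 0 is still created, change equals the later score, and percent change is undefined.

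**The case against.** The best case against this is that the size depends on a questionnaire that is not in the documents. A ticked box must be stored as missing, AIII and BIII must still be answered, and zero must apply to the item and not the domain. The ±50% limits also need AIII and BIII at opposite ends. This stands, and the conclusion is stated conditionally. The item reading is the better one, because Section 1 of the scoring table assigns values item by item, but it is not stated for Section 3.

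A rule specific to an instrument can fairly override the general no-imputation statements. That defends zero for an item left blank by accident. It does not defend zero for a patient who says that the question does not yet apply.

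SAP 6.0 limits percent change to where it is applicable, which plausibly covers a zero baseline. It does not cover negative ones. Listing 16.2.21 prints the boxes beside the scores, so a careful reader could trace affected values. The table would still carry them.

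A reader might go further than the documents allow in four ways:
- **That neither treatment score can be answered at baseline.** The expected items have no not-yet-treated box, and an expectation can be given before dosing.
- **That all of up to 24 patients are affected.** Nothing ties the INQoL word treatment to ATYR1940. The therapy and medication listings (16.2.6 and 16.2.7) carry disease-treatment flags, so some patients may have had earlier treatment to rate.
- **That the rule favours the drug.** The range is symmetric about zero.
- **That every Section 3 missing rule should go, or every unsure answer be set to missing.** The first alters the scoring of an instrument the SAP calls validated, without sight of its manual. The second keeps only patients with a definite opinion.

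**Conclusion.** The point holds for the perceived treatment score. The SAP has a response option that means no treatment yet, no rule for it other than zero, and a table of change from a visit before ATYR1940. On the stated assumptions the invented baseline lies between −50% and +50%, or is 0 if all four items are blank. Under the domain reading it is 0. In each case the no-baseline rule in SAP 6.0 is bypassed. Separately, percent change is unsuitable for both treatment scores, and that needs no assumption about the boxes.

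The reach is limited. The number of affected patients cannot be derived from the documents. Protocol 3.2.4 treats quality of life as exploratory with no specific endpoints, and SAP 9.0 plans no hypothesis tests. Of the 15 INQoL rows in Table 14.3.3, one has the invented baseline and two have the percent-change problem. The overall QoL score uses no Section 3 item, and no safety or immunogenicity output changes. It is worth correcting because a wrong number would be tabulated where no number exists.

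**What to change.** - **SAP 4.2.4:** set the perceived treatment score to missing at any visit where the not-yet-treated box is ticked. SAP 6.0 then withholds change without further wording.
- **Table 14.3.3, perceived score:** show actual values at visits after the first ATYR1940 dose, including the post-treatment follow-up visits, with no change from the pre-dose baseline.
- **Table 14.3.3, both treatment scores:** drop percent change, with a matching exception in SAP 9.7.2.
- **Table 14.3.3, expected score:** keep change from baseline.
- **Table 14.3.3, counts:** add the number of patients ticking the not-yet-treated or unsure box at each visit, so that readers can see how many scores rest on a non-answer.

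The cost is a few lines of SAP text and one table shell, with no new data collection. Table 14.3.4 already departs from the parent-study baseline for the FSHD-HI, so an exception for one instrument has precedent. The small downside is fewer scored values in the perceived domain.
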